### *Analysis of Secondary Outcomes*

The following outcomes will be summarized using mean  $\pm$  SD or median (IQR) and linear regression using the above described linear mixed model will be performed to assess the differences between treatment groups.

- ICU length of stay
- Hospital length of stay
- Time to shock reversal
- Time to liberation from mechanical ventilation
- Biomarker measures (regression controlled for baseline level of each biomarker)
- Muscle weakness score

The following outcomes will be summarized using frequencies and percentages and logistic regression will be performed to assess the differences between treatment groups.

- Neurologic outcome at hospital discharge
- Survival to hospital discharge

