### *Randomization and Intervention*

Patients were randomized to continuous NMB or usual care in blocks of four and in a 1:1 ratio. The randomization was stratified by study site and by the presence of shock, defined as the use of any vasopressor at the time of randomization. The random sequence was generated by an independent statistician who was not involved in the conduct of the study. The site-specific allocation sequences were maintained by the research pharmacies at each site for the duration of the study.

Patients in the continuous NMB arm received a rocuronium bolus of 1.0mg/kg followed by a continuous infusion of rocuronium for a total of 24-hours. The infusion of rocuronium was titrated to 1-2 out of 4 twitches on a train-of-four peripheral nerve stimulator. To minimize any difference in the time between randomization and receipt of the study drug between the two groups, patients in the usual care arm were administered a small volume of normal saline to mark the 0-hour time point. All patients undergoing TTM, including those who received continuous NMB, were deeply sedated per local site protocol. Use of the Columbia anti-shivering protocol was recommended to clinical teams, but adherence was not mandated.

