## Outcomes and Definitions

### *Primary Outcome and Sample Size Estimation*

The primary outcome of the study is change in serum lactate level measured between 0-hours and 24-hours after the receipt of study drug. This outcome was chosen as lactate is a continuous variable which is highly correlated with hospital survival in cardiac arrest patients. The 24-hour time point was selected as it was drawn after completion of the rocuronium infusion but not so late that a significant proportion of patients may have already died. Based on conservative estimates drawn from observational data, a sample size of 80 patients was specified to detect a predicted mean difference in 24-hour lactate of 2.0mmol/L ( $\pm 3.2$ mmol/L) with 80% power assuming a two-sided test and an alpha of 0.05.

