### *Secondary Outcomes*

- Lactate change between 0- and 12-hours after administration of study drug
- Lactate change between 0- and 36-hours after administration of study drug
- Shock-free days
  - Shock-free days measured as days alive and free of shock (<6 hours receiving a vasopressor) over the first 7 days after enrollment.

- Ventilator-free days
  - Ventilator-free days measured as days alive and free of invasive mechanical ventilation (<6 hours with an endotracheal tube) over the first 7 days after enrollment.
- Length of initial Intensive Care Unit (ICU) stay truncated at 28-days
  - Includes only the initial stay in the ICU and does not include ICU readmission
- Length of initial hospital stay truncated at 28-days
  - Includes only the initial hospital stay and does not include any readmissions
- Survival to hospital discharge
- Neurologic outcome at hospital discharge
  - As defined using the Modified Rankin Scale
- Biomarker measures (available at 0-hours and 24-hours)
  - Interleukin (IL)-1 $\beta$ , IL-6, IL-8, IL-10, and TNF- $\alpha$
  - Neuron specific enolase [NSE]
  - S100 calcium-binding protein B (S100B)
- Muscle weakness assessed using a modified Medical Research Council scale

A table of outcomes by treatment group will be included (see Appendix Table 3).

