## Statistical Analysis

### *General Principles*

All initial analyses will be performed in a modified intention-to-treat (modified ITT) population, defined as all randomly assigned subjects who received any study drug (rocuronium or the saline time marker). The primary analysis for the outcome of lactate at 24-hours will be repeated in the per-protocol population including only those patients who were alive at 24-hours and received either 24-hours of continuous rocuronium (if so assigned) compared to those who received usual care without any neuromuscular blockade medication after the time 0-hour point.

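### Shock-free and ventilator-free days are defined as secondary outcomes but not named in the analysis list, which names two times that are defined nowhere

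*SAP*

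**What the plan says.** The protocol and SAP agree on this point, so neither resolves the other.

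Under Secondary Outcomes, the first relevant definition is "Shock-free days measured as days alive and free of shock (<6 hours receiving a vasopressor) over the first 7 days after enrollment". The second is "Ventilator-free days measured as days alive and free of invasive mechanical ventilation", with a matching 6-hour allowance for an endotracheal tube and the same 7-day window.

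Under Analysis of Secondary Outcomes, neither count appears. The list contains "Time to shock reversal" and "Time to liberation from mechanical ventilation", and the method for that list is "linear regression using the above described linear mixed model will be performed to assess the differences between treatment groups". The model referred to is the one for lactate under Analysis of Primary Outcome: treatment, shock stratum, time point, treatment-by-time interaction, and a random intercept for site.

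Two other statements bear on the point. General Principles says "All initial analyses will be performed in a modified intention-to-treat (modified ITT) population", meaning randomized patients who received rocuronium or the saline marker. Randomization and Intervention stratifies by "presence of shock, defined as the use of any vasopressor at the time of randomization".

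**The concern.** A free-day count and a time to an event are different quantities. The count has a fixed window and takes account of death, because a day must be lived to be counted. The time needs a starting point, a defined event, and a rule for patients who die before the event or are never in the state that is supposed to end. The plan supplies none of these.

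A patient who dies on a vasopressor or ventilator never reaches reversal or liberation, and a linear model has no place for such a patient unless a value is assigned or the patient is left out. The planners recognised that deaths accumulate: they placed the lactate endpoint at 24 hours because it was "not so late that a significant proportion of patients may have already died". That remark concerns lactate, but these outcomes run past 24 hours.

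What is at stake is whether two secondary results are determined by the plan or by choices made at analysis. If results by arm are visible when the choice is made, the reader cannot tell which quantity was intended.

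**Working it through.** The plan gives no figure on this point to reproduce. The check compares the lists, then the definitions, and then illustrates the mechanics.

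**1. List match** (Secondary Outcomes against Analysis of Secondary Outcomes, both documents)

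| Outcome | Listed and defined | In analysis list |
|---|---|---|
| ICU stay, hospital stay, survival, neurologic outcome, biomarkers, muscle weakness (6) | yes | yes |
| Shock-free days, ventilator-free days (2) | yes | no |
| Lactate change to 12 h, to 36 h (2) | yes | no (not at issue here) |
| Shock-reversal time, ventilator-liberation time (2) | no | yes |

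Outcome list: 6 + 2 + 2 = 10. Analysis list: 6 + 2 = 8. In common: 6.

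**2. What is stated for each quantity**

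| Element | Free-day counts | The two times |
|---|---|---|
| Origin | enrollment | not stated |
| What is counted | a day alive with under 6 h of support | event not defined |
| Window | 7 days | not stated |
| Death | later days are not days alive; day of death not stated | not stated |
| Not on support at origin | counted like any other patient | not stated |

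**3. The two readings**

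- *Loose labels.* The counts are what is analysed, and the section names the wrong quantity. The favourable direction is also reversed: more free days is better, a shorter time is better.
- *Literal.* The counts have no named analysis, and the times are missing for patients who die on support. A patient without a vasopressor at randomization has no shock at the origin, but may start one later and come off it, or may never need one.

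On either reading, the lactate model's time-point and interaction terms cannot apply to an outcome measured once.

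**4. Mechanics only: four invented patients**

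Days are 24-hour blocks, and reversal is taken here as the end of vasopressor use. A: vasopressor stops at 29 h, alive at day 7. B: never on a vasopressor, alive at day 7. C: dies at 60 h on a vasopressor. D: vasopressor stops at 48 h, dies at 100 h.

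Mean shock-reversal time:
- B and C left out: (29 + 48)/2 = 38.5 h, n = 2
- B set to 0, C left out: (29 + 0 + 48)/3 = 25.7 h, n = 3
- B left out, C set to 168 h: (29 + 168 + 48)/3 = 81.7 h, n = 3
- B set to 0, C set to 168 h: (29 + 0 + 168 + 48)/4 = 61.3 h, n = 4

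Mean shock-free days, always n = 4 (A has 5 h of vasopressor on day 2, so that day counts as free):
- Day of death not counted: (6 + 7 + 0 + 2)/4 = 3.75
- Day of death counted: (6 + 7 + 0 + 3)/4 = 4.00

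The time depends on an unstated rule and uses between 2 and 4 of the 4 patients. The count uses all four, and only the day of death is open.

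**5. Can the linear model stay for the counts?**

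Assumed inputs: 80 patients, 5 sites, blocks of four within site and shock stratum, 60% in shock, no treatment effect. The count is 0 in 30%, 50% or 70% of patients (15 points higher with shock) and otherwise uniform on 1 to 7. The model is linear regression on treatment, shock and site, with fixed site effects standing in for the random intercept; 5,000 runs each. Two-sided rejection at 0.05 was 4.9%, 5.2% and 4.9% (Monte Carlo standard error 0.3 points). A second run on the same inputs gave 5.1%, 5.4% and 4.5%. This supports the remedy for type I error only; it says nothing about the size of the defect.

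**The case against.** The strongest reply is that this is loose labelling. Each list has exactly one shock item and one ventilator item, and every other item in the analysis list matches a listed outcome. On that reading the outcome section gives the definition, the analysis section gives the method, and a reversed direction changes only how the sign is read. This may well be what was meant. No passage says so, however, and the text still names the wrong quantity.

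A second reply is that the modified ITT rule says who is analysed. It does not require every outcome to have a value for every patient; muscle weakness also cannot be scored in patients who die before assessment. That stands, so the rule alone does not make the two times unworkable. The missing definitions do.

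A reader might be tempted to infer more than the documents support:

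- *That the two definitions of shock conflict.* One sets a baseline stratum and the other says when a day counts as free. They serve different purposes. What is missing is a definition of reversal.
- *That patients in the no-shock stratum can have no event.* The stratum is fixed at randomization, and a vasopressor may be started later.
- *That any death might score zero free days.* The definition counts days alive, and nothing in it voids days lived before a death.
- *That absence from Appendix Table 3 shows the outcomes were dropped.* That shell also omits the biomarkers.

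**Conclusion.** The point holds. Two of the 10 listed secondary outcomes are not named in the analysis list, and two of the 8 items in that list have no definition. This rests on the text alone, and an edit is needed on either reading.

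Its effect on results is unknown. The documents give no mortality or shock-share figures, and the invented patients show only that the answer depends on the rule chosen. A reader might infer bias between the arms, or a deliberate switch of outcomes; the documents support neither. The primary outcome and the sample size are untouched. This should be fixed, because the discrepancy is certain and the correction is cheap, but it does not threaten the trial's main conclusion.

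**What to change.** In both documents:

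- Under Analysis of Secondary Outcomes, replace the two time lines with shock-free days and ventilator-free days as already defined. Every modified ITT patient with vital-status and support data then has a value.
- Analyse them with treatment, shock stratum and a site random intercept, without the time-point and treatment-by-time terms.
- Under Secondary Outcomes, state that days after death count as not free, as the definition already implies, and how the day of death is scored.
- If a time-to-event version is kept, define its origin, event, window and population, and treat death as a competing event.
- Date the change, and label it post hoc if results by arm have been seen. Enrollment and conduct are described in the past tense, so this record matters.

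Rows for the two counts in Appendix Table 3 are optional.

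The cost is two replaced lines, a short note on the model terms and a sentence on scoring. No new data are needed, since the existing definitions already require vasopressor, ventilator and vital-status data. The downside is that free days combine death with organ support, so they must be read beside survival, and a mean of a 0-to-7 count is a coarse summary.

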# **Outcomes and Definitions**

## Primary Outcome and Sample Size Estimation

The primary outcome of the study is change in serum lactate level measured between 0-hours and 24-hours after the receipt of study drug. This outcome was chosen as lactate is a continuous variable which is highly correlated with hospital survival in cardiac arrest patients. The 24-hour time point was selected as it was drawn after completion of the rocuronium infusion but not so late that a significant proportion of patients may have already died. Based on conservative estimates drawn from observational data, a sample size of 80 patients was specified to detect a predicted mean difference in 24-hour lactate of 2.0mmol/L (±3.2mmol/L) with 80% power assuming a two-sided test and an alpha of 0.05.

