## Study Overview

### *Study Design and Setting*

This was a phase II, multi-center, randomized trial of continuous neuromuscular blockade using rocuronium vs. usual care in patients who had sustained return of spontaneous circulation (ROSC) but remained unresponsive after cardiac arrest. Enrolling sites were five urban tertiary care centers in the United States. The trial coordinating center gathered and analyzed the data, and vouches for the accuracy and completeness of the data and for the fidelity of the trial to the protocol. Written informed consent was obtained from the legally authorized representatives of all patients.

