### *Analysis of Primary Outcome*

The primary outcome is lactate change between 0-hours and 24-hours after enrollment. The group difference in change from the time of study drug administration (0-hours) to 24-hours will be assessed using a linear mixed effects model. Lactate values will be log-transformed for this analysis if they are not approximately normally distributed. Fixed effects will include the allocated treatment, shock stratification, time point (0-hour, 12-hour, and 24-hour), and the interaction between treatment and time point. Study site will be included as a random intercept. The usual care group will be the reference variable for group, and baseline (0-hour) will be the

reference variable for time. Means and 95% confidence intervals of lactate over time will be presented, by treatment, using longitudinal plots (see appendix Figure 2)

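### The logistic models for survival and neurologic outcome name no stratification factor; followed literally they ignore shock and site, which costs a little power if shock is prognostic

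*SAP*

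**What the plan says.** The relevant wording is the same in the Protocol and the SAP.

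- Design (Randomization and Intervention): "The randomization was stratified by study site and by the presence of shock". Allocation: "Patients were randomized to continuous NMB or usual care in blocks of four and in a 1:1 ratio". Study Design and Setting: "Enrolling sites were five urban tertiary care centers in the United States".
- Primary model (Analysis of Primary Outcome): "Fixed effects will include the allocated treatment, shock stratification, time point", plus the treatment-by-time interaction. For the other design factor: "Study site will be included as a random intercept".
- Continuous secondary outcomes (Analysis of Secondary Outcomes): "linear regression using the above described linear mixed model will be performed". By that reference they inherit shock and site.
- Survival and neurologic outcome (same section): "logistic regression will be performed to assess the differences between treatment groups". No covariate is listed and there is no reference back to the primary model. The General Principles section contains no rule that fills the gap.

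The section does name an adjustment where one is meant: the biomarker regressions are to be controlled for the baseline level.

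**The concern.** Stratified randomisation balances the arms on shock and so removes between-stratum variation from the treatment comparison. A treatment-only logistic model does not know this. Its standard error still includes that variation, so if shock is prognostic the error is too large for the estimator it accompanies, and the test rejects less often than its nominal level.

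At stake is some power for the two secondary outcomes that matter most to patients, in a trial sized for lactate. A second issue is that silence on covariates leaves the choice between an adjusted and an unadjusted analysis open until the data are seen. It also leaves unsaid which kind of odds ratio the effect-estimate column of Appendix Table 3 will show.

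**Working it through.** **The plan's own figure.** The only power statement concerns lactate: "a sample size of 80 patients was specified to detect a predicted mean difference in 24-hour lactate of 2.0mmol/L", with SD 3.2, two-sided alpha 0.05 and 80% power. Per arm, n = 2(1.960 + 0.842)² × (3.2/2.0)² = 2 × 7.85 × 2.56 = 40.2, so 41 per arm or 82 in all. With 40 per arm, power is 79.8% (normal) or 78.8% (t-test). The stated 80 is reproduced closely enough. No power figure is given for the binary outcomes.

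**Inputs.** From the documents: 80 patients, five sites, blocks of four within site by shock, 1:1. Assumed, because the documents give none: shock prevalence, survival by shock status and treatment effect. Main scenarios: 50% in shock, conditional treatment odds ratio (OR) 3.5.

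**Simulation.** Treatment only versus treatment + shock; two-sided Wald tests at 0.05; 6,000 trials per scenario. Ranges are across repeated runs.

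| Usual-care survival, no shock / shock | Type I error, without vs with shock | Power, without vs with shock |
|---|---|---|
| 60% / 20% | 3.7–3.9% vs 4.9–5.3% | 65–66% vs 70–71% |
| 55% / 25% | 4.2–4.4% vs 5.0–5.1% | 72% vs 74% (gain 1.5–2 points) |
| 50% / 35% | not tabulated | gain under 1 point |

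The simulation standard error is √(0.05 × 0.95/6000) = 0.28 points for type I error and √(0.65 × 0.35/6000) = 0.62 points for power.

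**Why the test is conservative (60%/20%, no treatment effect).** Overall survival is 40%, so the unadjusted model uses a variance of 0.40 × 0.60 = 0.24 per patient. Within strata the average is (0.60 × 0.40 + 0.20 × 0.80)/2 = 0.20. With perfect balance on shock, the effective critical value would be 1.96 × √(0.24/0.20) = 2.147, a type I error of 3.2%. Ten cells averaging eight patients leave some blocks incomplete, so balance is not perfect. The simulated model SE is 0.463 against a true SD of 0.435. Then 1.96 × 0.463/0.435 = 2.086, which gives 3.7%, as in the table.

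**What the unadjusted odds ratio estimates.** Apply OR 3.5 within each stratum and average:

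- 60%/20%: odds 1.5 × 3.5 = 5.25 (84.0%) and 0.25 × 3.5 = 0.875 (46.7%). The mean is 65.3%, odds 1.885. Against usual-care odds of 0.40/0.60 = 0.667, the marginal OR is 2.83.
- 55%/25%: treated survival 81.1% and 53.8%, mean 67.4%, odds 2.072; marginal OR 2.072/0.667 = 3.11.
- 50%/35%: treated survival 77.8% and 65.3%, mean 71.6%, odds 2.516; marginal OR 2.516/0.739 = 3.40.

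In the first case the simulated unadjusted median was 2.8, which is on target for the marginal effect. The adjusted median was about 3.7, slightly above the conditional 3.5.

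**Interval width.** Adding shock raises the SE of the log OR: 0.471 to 0.549 at 60%/20%, and 0.475 to 0.518 at 55%/25%. Power improves because the conditional log OR is larger by more than the SE grows, not because the interval shrinks.

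**Sensitivity to the shock effect.** 60% in shock, 40% overall usual-care survival, conditional treatment OR 3, about 5,000 trials each:

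| OR of survival for shock | Type I error, without shock | Power, without vs with shock | Marginal OR |
|---|---|---|---|
| 1.0 | 4.9% | 68.1% vs 68.0% | 3.00 |
| 0.5 | 4.1% | 67.2% vs 67.3% | 2.91 |
| 0.33 | 4.3% | 64.1% vs 65.5% | 2.79 |
| 0.2 | 3.5% | 57.2% vs 60.9% | 2.59 |
| 0.1 | 2.6% | 46.2% vs 54.7% | 2.29 |

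With shock in the model, type I error is 4.6% to 5.0% throughout. At shock OR 0.33, prevalences of 40% and 80% give power gains of 1.3 and 0.0 points.

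**The case against.** **The plan is silent, not unadjusted.** A reader might infer that the SAP prescribes a treatment-only model. It does not say so. The sentence for the continuous outcomes closes with the same words about assessing group differences, yet its model contains shock and site, so those words cannot by themselves mean treatment only. This stands: the defect is a missing specification. But an analyst who follows the sentence as written would fit treatment alone.

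**The smaller odds ratio is not bias.** A reader might conclude that the unadjusted analysis dilutes the effect. The odds ratio is non-collapsible: 2.83 and 3.5 are correct answers to different questions, and the documents do not say which is wanted. This stands in full.

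**Adjustment does not tighten the interval.** Also correct. The unadjusted interval is conservative only relative to its own estimator's sampling variability.

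**The size is assumed.** The 60%/20% case is a shock odds ratio of 0.25/1.5 = 1/6, which is strong. Nothing in the documents shows that shock is this prognostic, although stratifying on it, adjusting the primary model for it and listing it as a subgroup show that the trial takes it seriously. At a treatment OR of 2, power without and with shock is only 24% vs 28% (60%/20%), 28% vs 29% (55%/25%) and 34% vs 34% (50%/35%). These comparisons are weak whichever model is used.

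**Site was not tested.** The fitted models had no site term, so the figures say nothing about a five-site random intercept with 80 binary outcomes. Including site rests on consistency with the primary model, and a fallback is needed.

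**Conclusion.** The point holds as a mismatch between design and analysis that costs almost nothing to repair. The logistic sentence names neither stratification factor, while the other regression models for outcomes carry both. If shock is prognostic, following the sentence literally gives a conservative test. Under the assumptions above the power loss is about 5 points at 60%/20%, 1.5 to 2 at 55%/25%, and under 1 at 50%/35%; with no shock effect there is no loss. A reader should not infer inflated false positives: the error runs the other way.

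Severity is low to moderate. The outcomes are secondary, the trial is phase II, and the size depends on a shock effect the documents do not give. The simulations are framed as survival. They carry over to neurologic outcome only by analogy, because no cut-point is defined for it: the outcome list uses the modified Rankin Scale while Appendix Table 3 shows CPC ≤2, and these need to be reconciled before any logistic model can be fitted.

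**What to change.** Add one sentence to Analysis of Secondary Outcomes, in both documents, along these lines: *Logistic models for survival and neurologic outcome will include allocated treatment and the shock stratum as fixed effects and study site as a random intercept, as in the primary model; if the site term does not converge it will be dropped and shock retained. The odds ratio and 95% confidence interval will be reported as conditional on these factors.*

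The cost is one sentence, one extra fixed-effect parameter and a site term that can be dropped. The shock stratum is already collected and appears in Appendix Table 1. If shock proves unimportant the power penalty is negligible (68.1% vs 68.0% at shock OR 1). Fixing the covariates in advance also settles which odds ratio Appendix Table 3 will show. If the team prefers a marginal effect, it should say so and state how the stratification will be reflected in its standard error.
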